The trial will enrol healthy adults (18-65 years) that are employed by any Hamilton Health Sciences site (Chedoke, Hamilton General Hospital, Juravinski Hospital, Juravinski Cancer Centre, McMaster University Medical Centre, McMaster Children’s Hospital, West Lincoln Memorial Hospital, St. Peter’s Hospital). Individuals will be excluded from the trial if (1) they are unable to or express an unwillingness to comply with core components of our study protocol (i.e. blood draws, fitness assessments, diet plan, workout plan) or if (2) they have a cardiovascular disease or insulin-dependent diabetes. See Table 1 for the full eligibility questionnaire form and schema. There could be a delay between the time when someone completes the eligibility questionnaire form and the time of official enrollment. As such, potential study participants will be told to contact the study team should any of their responses to the eligibility questionnaire change and will also be prompted before performing their baseline assessment (data collection sheet, blood draw, and fitness assessment).

Table 1. Eligibility Questionnaire Form

Number	Question	Exclude if response is:
1	Are you employed by Hamilton Health Sciences?	No
2	Would you be willing to attend a GoodLife Fitness centre in Hamilton or Ancaster?	No
3	Are you planning to take vacation for more than 2 weeks from May 1, 2018 to July 31, 2018?	Yes
4	Are you currently pregnant, breastfeeding or planning to be pregnant from May 1, 2018 to July 31, 2018?	Yes
5	Are you currently taking insulin?	Yes
6	Have you ever had a bone marrow transplant?	Yes
7	Have you ever had a stroke, heart attack, coronary artery bypass graft (CABG) surgery, peripheral artery disease, or coronary angioplasty?	Yes
8	Are you currently taking any of the following medications: blood thinners (e.g. warfarin), ACE inhibitors (e.g. captopril, enalapril, lisinopril, moexipril, quinapril, ramipril), antibiotics (e.g. linezolid), antidepressants (e.g. phenelzine, tranylcypromine)	Yes
9a	One aspect of lifestyle that we are hoping to enhance is physical fitness. If you participate in the trial, you will receive a personalized workout plan. Are you willing to comply to a trainer-approved workout plan from May 1, 2018 to July 31, 2018?	No
9b	Are you willing to perform two physical fitness assessments (baseline and 3 months later)?	No

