9c	Do you currently have any conditions that restrict your ability to exercise regularly (e.g. osteoarthritis, knee injury, chronic back pain, arrhythmia)?	Yes
10a	If you participate in the DNA ^{ble} trial, you will receive a personalized meal plan. Are you willing to comply to a dietician-approved meal plan from May 1, 2018 to July 31, 2018?	No
10b	Do you currently have any dietary restrictions due to food sensitivities (e.g. gluten, soy, peanuts, eggs, shellfish, etc.), preferences (e.g. vegetarianism, veganism), or medical conditions (e.g. Crohn's disease, bulimia nervosa)?	Yes

11	Blood biomarkers, such as lipid and fasting glucose levels, will be tested to monitor changes in your cardiovascular health. Are you willing to have blood testing performed by a medical professional in a hospital setting on two separate occasions: at baseline and 3 months later?	No
----	---	----

Participant Benefits and Risks

The major incentive for Hamilton Health Sciences employees to participate in this trial is that they will be equipped with new tools designed to improve their fitness and dietary habits. Specifically, study participants will receive personalized exercise plans, meal plans, a 3-month GoodLife Fitness gym membership, and their genetic results. Conversely, major risks of participating in this trial include unintended disclosure of personal information and injury from performing exercises. Protocols have been built-in to reduce mitigate these risks and are detailed in subsequent sections. In accordance with Good Clinical Practice, all study participants may exert their right to withdraw from the trial at any point in time for any reason with no obligation to reveal the reason for discontinuation.

Study Methodology & Workflow

[figure not shown]

Figure 1. DNABLE study workflow.

Advertising, Marketing, Recruitment

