An electronic questionnaire form will be sent to all individuals that have expressed interest in participating in the trial. This questionnaire will determine their eligibility for trial participation. Individuals that meet all eligibility requirements will be provided with (1) a study information sheet providing further details about the trial (e.g. information on the intervention) and (2) consent form. To allow for timely collection of informed consent data from multiple centres, we propose to administer consent through an electronic form. Electronic informed consent will adhere to guidelines outlined by the FDA (<https://www.fda.gov/downloads/drugs/guidances/ucm436811.pdf>). As with paper consent, individuals will be asked to initial, date, and sign each section of the consent form. A member of the trial team will be available Monday to Friday during work hours to answer any questions or concerns about the consent form or study via telephone and e-mail. Paper consent forms will also be made available at each study site if individuals are uncomfortable with electronic consent. The first 500 eligible and consenting individuals will be selected for participation in the trial. Subsequently, a follow-up questionnaire gathering demographic information for the purposes of logistical planning and to help to inform the randomization scheme will be issued.

Baseline Assessment

The baseline assessment will be identical for participants assigned to either the intervention or control group and will consist of: (1) completing the study report form, (2) a blood draw which will provide biological material for laboratory testing, (3) and a low-risk fitness assessment which does not involve any physical activity. The study report form will collect information pertaining to demographics, medical history, dietary habits, physical activity levels, mental health and wellbeing, as well as attitudes, feelings, and competency regarding genetic testing. The fitness assessment will involve a simple series of measurements including central adiposity (waste-to-hip ratio), heart rate, blood pressure, and strength (e.g. calf circumference, bicep circumference). To eliminate any possibility of assessment bias during the first assessment, intervention assignment will not occur until after the baseline assessment has been completed.

Randomization

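### The text excludes people who have a cardiovascular disease, but the form that decides eligibility asks about it directly only through a closed list of five

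*Combined protocol and SAP*

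**What the plan says.** Trial Population in the combined protocol and SAP gives two grounds for exclusion. The second is that "they have a cardiovascular disease or insulin-dependent diabetes. See Table 1 for the full eligibility questionnaire form and schema". The term is not defined further in the text.

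Eligibility, Consent, and Enrollment makes the form the operating instrument: "This questionnaire will determine their eligibility for trial participation".

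Three items in Table 1 bear on cardiovascular disease:
- Question 7: "Have you ever had a stroke, heart attack, coronary artery bypass graft (CABG) surgery, peripheral artery disease, or coronary angioplasty".
- Question 8 excludes users of certain medicines, among them "blood thinners (e.g. warfarin), ACE inhibitors".
- Question 9c: "Do you currently have any conditions that restrict your ability to exercise regularly (e.g. osteoarthritis, knee injury, chronic back pain, arrhythmia".

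Because time may pass between the form and enrolment, people are asked to contact the team "should any of their responses to the eligibility questionnaire change and will also be prompted before performing their baseline assessment". The baseline study report form then records medical history among other things, and assignment follows only once the baseline assessment is complete.

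**The concern.** The written exclusion is general, while the direct question that applies it is a fixed list. A respondent whose heart disease is not on that list can truthfully answer No to question 7. If questions 8 and 9c do not catch the person either, the form returns an eligible result for someone the text says should be out.

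What is at stake is safety and consistent screening. Every participant gets gym access, and the intervention arm also gets five 30-minute workouts a week. The protocol itself lists injury from exercise among the major risks of taking part.

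**Working it through.** No formula applies and the plan gives no figure to reproduce, so the check compares the text criterion with each item and each later step.

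**Items on the form.** Table 1 has questions 1, 2, 3, 4, 5, 6, 7, 8, 9a, 9b, 9c, 10a, 10b and 11, which makes 14.
- Direct cardiovascular items: 1 (question 7). It names 5 events or conditions: stroke, heart attack, bypass surgery, peripheral artery disease and angioplasty. It has no example marker and no 'other' option, whereas questions 8, 9c and 10b all give open examples.
- Partial, indirect items: 2. Question 8 works only through a listed medicine. Question 9c is open-ended and names arrhythmia, but only for conditions that restrict regular exercise.
- Items asking about any other cardiovascular disease: 0.

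**A respondent traced through the form.** Take a person with diagnosed valve disease, cardiomyopathy, or angina without a heart attack or revascularisation. The person takes no blood thinner, ACE inhibitor or other listed medicine and feels able to exercise. The answers are No to question 7, No to question 8 and No to question 9c. If the remaining answers also qualify, the form gives no reason to exclude.

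**Steps after the form.** Five have visible content:
1. The follow-up questionnaire, described as "a follow-up questionnaire gathering demographic information for the purposes of logistical planning and to help to inform the randomization scheme will be issued". Eligibility is not among its stated uses.
2. The prompt before baseline. It concerns changed answers to the same form, and a question that was never asked has no answer to change.
3. The baseline medical history. It could reveal the diagnosis before assignment, but no exclusion is written at that point.
4. Laboratory findings (Incidental Findings). They act on abnormal blood values, with continuation left to the physician's discretion and the participant's willingness.
5. Fitness-assessment findings (Incidental Findings). They act on measured blood pressure or heart rate and stop only the fitness portion.

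So 0 of 5 are stated to exclude on a reported cardiovascular diagnosis. Two of 5 (steps 4 and 5) state a consequence for continuing, and both act on measured values.

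**The case against.** The strongest reply is that Table 1 is itself the definition. The reference to it comes straight after the exclusion, it has a column giving the excluding response, and it lists several grounds that the prose omits, such as pregnancy and bone marrow transplant. On that reading the prose is a summary and there is no contradiction. This is a fair reading and cannot be ruled out. But the text does not state it, and question 9c's mention of arrhythmia shows that the form already looks beyond question 7's list. Even if it is right, the traced respondent still passes into an exercise trial, so the screening point survives as an improvement.

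A second reply is that the Trial Population rule binds throughout and need not be repeated at each step. That stands. Staff who see a diagnosis in the baseline medical history could apply the rule before assignment. A reader might infer from the step count that nothing after the form can exclude such a person. The documents do not support that. They show only that the action is not written at baseline and so depends on staff making the connection.

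A third reply is that the group is narrow and protected in other ways. Question 9c catches disease that limits exercise. There is a gym orientation, advice on supervision, permission to forgo an exercise, and a stop for very high blood pressure or heart rate. This also stands, and it keeps the point small. These measures lower risk for everyone, but they do not apply the exclusion.

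**Conclusion.** The concern holds as a minor one. Of 14 items, one asks directly about cardiovascular disease through five named events or conditions, and two more catch some other cases. A person with a different cardiovascular disease, no listed medicine and no reported restriction passes the form. Whether this contradicts the protocol depends on question 7 not being the intended definition of the term, on which the text is silent.

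The number of people affected and the remaining exercise risk cannot be derived from the documents, and no effect on power or the primary result is claimed. The conclusion covers Table 1 and the visible text only. The recruitment materials, information sheet, consent form and workflow figure could not be checked.

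A reader might also infer that the 18-65 age limit goes unenforced because no item asks age. The documents do not support that. The limit binds as written, and age is known before assignment because the minimisation scheme balances on it.

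**What to change.** Keep question 7's existing list and add: *or do you currently have any other diagnosed heart or arterial disease (e.g. angina, heart failure, valve disease, cardiomyopathy, aneurysm)? High blood pressure alone does not count here.* The clause asks about current disease because the text exclusion is in the present tense. Leave question 8 unchanged, and ask the extended question again at the existing prompt before the baseline assessment, so that it acts before assignment.

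If the sponsor does intend question 7 to define the term, one sentence in Trial Population saying so would remove the inconsistency. It would not screen out the traced respondent, so the added clause is preferable.

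The cost is one extended item on an electronic form. A few more respondents would be screened out, and the high-blood-pressure exception should help keep that number small. Since "The first 500 eligible and consenting individuals will be selected for participation in the trial", those screened out on the form are replaced by the next eligible people who consent, and the planned size is unaffected as long as enough people come forward.

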Participants will be randomized to intervention or control groups using a minimization scheme which will adaptively weight probabilities of treatment assignment based on the distribution of age (≥ 40 vs. < 40), gender (male vs. female), and ethnicity (European/African/East Asian/South Asian/Latino/Other). This design has been adopted to minimize unintended covariate biases, which can plague smaller trials. Randomization will be implemented through a centralized database. The intervention will be delivered via automated e-mails, minimizing direct personal contact with the intervention group.

Controls

Upon completion of all three components of the baseline assessment, the control group will receive access to a GoodLife fitness centre of their choosing or if not specified, the location nearest to their home. For safety purposes, an orientation will be provided by GoodLife Fitness staff to all study participants. This will serve to demonstrate best practices within the gym, including how to

properly operate the fitness equipment, what the appropriate footwear and workout attire is, and general operating rules within the gym. To further ensure the safety of study participants when exercising, it will be emphasized that (1) exercises should be performed with some form of supervision when attempting a new exercise or heavy weight (e.g. a GoodLife Fitness staff member to spot), (2) to never perform types of exercises they may be uncomfortable with, and (3) to never attempt to exercise using an excessive amount of weight. Study participants may also consult GoodLife Fitness staff if they have questions about how to perform a specific exercise.

Intervention

In addition to a free gym membership for the duration of the trial (all participants, irrespective of randomization, will receive a free gym membership), the intervention group will receive (1) their genetic results, (2) personalized workout plan and (3) personalized meal plans, all of which will be delivered through a secure web portal accessible via smartphone or computer. See the “data privacy and security” section below for details regarding specific security measures for the web portal.

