The genetic results provided to study participants will consist of scores ranging from 0 to 100 based on the population percentile of the combined effects of many (up to several hundreds of thousand) genetic variants, herein referred to as polygenic scores (PGS). The aim of the PGS is to provide participants with entertaining yet scientifically sound and accurate genetic information to encourage the pursuit of healthy living and identify healthy lifestyle habits that best fit each individual. PGS for approximately twenty traits related to health, fitness and nutrition will be provided to study participants. These traits are chosen for their relevance to healthy lifestyle habits (e.g. genetic predisposition to adiposity or muscle strength), entertainment value (e.g. preference for mornings) or both (e.g. bitterness taste perception, which while entertaining can also help guide vegetable choices). None of the PGS are diagnostic and are therefore not medically actionable.

The personalized workout plan includes 5 x 30-minute exercise programs per week, which is in line with the Canadian recommendation of 150 minutes of moderate to vigorous physical activity per week. The programs will propose a set of specific exercises to perform including the number of sets and repetitions. All workout programs have been approved by GoodLife Fitness and developed by a professional trainer to the UK Olympic team and sports scientist, [name]. Through the web platform, instructional videos describing and showing how to perform each exercise will be made available. It will be emphasized that if at any point a study participant feels uncomfortable with an exercise, the participant should consult an on-site personal trainer or forego the exercise altogether.

The personalized meal plans are approved by a registered dietician and are consistent with the Canadian recommended dietary allowances (RDA). If new, unexpected food allergies develop throughout the course of the trial, these will be taken into consideration and dietary recommendations for this particular individual will be adjusted immediately. Depending on the severity of the allergy, the study participant may be referred to a doctor for allergy testing.

Final assessment

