The 3-month follow-up assessment will be identical for participants assigned to either the intervention or control group and will consist of: (1) completing the exit study report form, (2) a blood draw which will provide biological material for laboratory testing, and (3) a low-risk fitness assessment which does not involve any physical activity (Table 2). The exit study report form will

strongly resemble the original baseline study report form and query information pertaining to demographics, medical history, dietary composition, physical activity levels, mental health and wellbeing, as well as attitudes, feelings, and competency regarding genetic testing. Laboratory testing will not include genetic testing (as this would be completed using the blood samples collected at baseline) but will include testing of lipoproteins, fasting glucose, and inflammatory markers as conducted in the baseline assessment.

To incentivize study participants to complete their final assessment, they will receive: 1) an additional month's worth of exercise and meal plans and 2) a lifetime subscription to the GeneBlueprint web portal which will be updated with new genetic prediction scores and health tools over time. Furthermore, individuals in the control group will be provided access to their genetic results, personalized meal plan, and personalized workout plan upon trial completion.

Endpoints

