All analyses conducted will follow the “Intention-to-treat” (ITT) principle to avoid biases due to differential adherence or loss-to-follow-up. In other words, no post-hoc exclusions will be made; study participants will be analyzed according to the group to which they were initially assigned even if they did not receive the intended treatment (e.g. due to injury during trial period impeding ability to exercise) or did not comply. Descriptive characteristics of each group will be summarized as the mean, standard deviation and 95% confidence-interval for continuous variables and using frequencies and percentages for categorical variables. Statistical tests will be two-sided, and between-group comparisons will be presented with 95% confidence intervals where possible. The statistical significance level set will vary depending on the number of statistical tests performed. Multiple hypotheses testing will be adjusted for within analyses of primary and secondary endpoints using a Bonferroni-corrected p-value threshold.

Baseline characteristics

Baseline characteristics will be compared using univariate regression to assess the balance of key risk factors between the intervention and control groups. Linear regression will be applied for continuous variables (age, blood pressure, waist-to-hip ratio, body fat percentage, total weekly

physical activity level, and dietary risk score) logistic regression for dichotomous variables (gender, smoking status, diabetes, dyslipidemia), and analysis of covariance (ANCOVA) will be applied for categorical variables exceeding two factor levels (ethnicity, hospital site). Intervention status will be the independent variable in the regression model. Differences in the mean or proportion of categories between groups will be considered statistically significant if the P-value is less than 0.05.

Primary Endpoints

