The primary endpoints are changes in physical activity levels as well as dietary risk score (DRS) from baseline to follow-up. Between-group differences in primary endpoints will be evaluated through linear regression. Weekly physical activity level will be represented as a continuous variable (frequency of strength training and aerobic exercise per week) for the primary analysis. Baseline characteristics found to be differentially distributed between intervention and control groups will be included as covariates in subsequent models. Between-group differences for changes in dietary risk score will be assessed through linear regression again adjusting for covariates. The significance threshold for physical activity levels and dietary health will be 0.025 given that two primary endpoints are tested.

Subgroup analysis will be conducted to explore whether changes in dietary health and physical activity levels differ based on key strata (age > 40 vs. age < 40, ethnicity, gender, baseline low/med/high physical activity levels and baseline dietary risk score tertiles). For example, it is conceivable that individuals who begin with the lowest activity levels and least healthy diets have the derive more benefit from personalized health recommendations, whereas others who already adhere to healthy lifestyle behaviours may have an attenuated response to our intervention.

Secondary Endpoints

Between-group differences in changes in levels of dyslipidemia (triglycerides), dysglycemia (fasting glucose), inflammation (C-reactive protein), blood pressure, measures of fitness (waist-to-hip ratio, circumference of thigh, calf, and bicep, body fat percentage) and overall cardio-metabolic risk as estimated by IHMRS will be analyzed using linear regression. Model covariates will include any baseline characteristics found to be differentially distributed between intervention and control groups. These analyses are considered exploratory and the significance threshold will thus be set at 0.05 for suggestive association and 0.005 (i.e. Bonferroni correction for 10 tests) for definitive association.

Technical Considerations

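### Exercise injury is named as a major risk and the workout plan goes to one arm only, but the trial plans no systematic recording or between-arm reporting of injuries and leaves its wellbeing data unanalysed

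*Combined protocol and SAP*

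**What the plan says.** **The risk.** Participant Benefits and Risks says that "major risks of participating in this trial include unintended disclosure of personal information and injury from performing exercises". It adds: "Protocols have been built-in to reduce mitigate these risks and are detailed in subsequent sections". The same section lets participants withdraw "with no obligation to reveal the reason for discontinuation".

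**The response to the risk.** The Controls section says: "For safety purposes, an orientation will be provided by GoodLife Fitness staff to all study participants". It also gives advice on supervision and on avoiding unfamiliar or heavy lifts. The Intervention section adds instructional videos and leave to skip an exercise. Table 1 (item 9c) screens out people with conditions that limit exercise, and the fitness part of Incidental Findings deals with extreme blood pressure or heart rate at baseline.

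**The difference between arms.** Both arms get gym access. "The personalized workout plan includes 5 x 30-minute exercise programs per week", and this plan, the meal plan and the genetic results reach controls only after their trial period.

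**What is collected and analysed.** The exit form is to "strongly resemble the original baseline study report form and query information pertaining to demographics, medical history, dietary composition", as well as activity, mental health and wellbeing, and attitudes to genetic testing. The Baseline Assessment form covers essentially the same topics. The primary endpoints are activity and diet. The secondary analysis covers "Between-group differences in changes in levels of dyslipidemia (triglycerides), dysglycemia (fasting glucose), inflammation (C-reactive protein), blood pressure, measures of fitness" and a cardio-metabolic risk score. In the Data Analysis Plan, injury occurs once, in the Overview, as an example of why someone might not receive the intended treatment: "due to injury during trial period impeding ability to exercise".

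**The concern.** The protocol names a major risk, expects that some participants may be injured badly enough to stop exercising, and randomises people to an exercise prescription or to gym access alone. That design can estimate the excess of injury attributable to the programme, but only if injuries are asked about in the same way in both arms. If they are not, the information cannot be recovered at analysis.

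The same holds, more cheaply, for psychological effects. The data come from both arms at both visits, and controls do not see their genetic results until after the exit form. A randomised comparison of wellbeing is therefore available without further data collection, but none is planned.

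At stake is the balance of the final report. A gain in exercise frequency would be published without an injury rate beside it, in a trial whose own protocol calls injury a major risk.

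**Working it through.** **1. The plan's own figure.** The only design figure is 90% power for a 0.32 SD difference with 250 per arm at two-sided alpha 0.025. Power = Φ(0.32 × √(250/2) − 2.241) = Φ(3.578 − 2.241) = Φ(1.336) = 0.909. It reproduces, but it concerns the efficacy endpoints. No figure for injury is stated, so every injury rate below is an assumption.

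**2. Tracing injury and wellbeing through the plan.**

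| Place | Injury | Wellbeing |
|---|---|---|
| Participant Benefits and Risks | named as a major risk | not named |
| Controls, Intervention | prevention only | – |
| Baseline and exit forms (listed topics) | not named; medical history is listed | collected at both visits |
| Endpoints; Primary and Secondary Endpoints | absent | absent |
| Data Analysis Plan, Overview | example under intention-to-treat only | absent |
| Incidental Findings | laboratory results, and baseline heart rate and blood pressure only | absent |

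No section defines an injury, records it systematically, or compares it by arm.

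**3. Precision if injuries were recorded.** With the same proportion p injured in each arm and n per arm responding, the 95% CI half-width for the difference is 1.96 × √(2p(1 − p)/n).

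- p = 5%, n = 250: 1.96 × √0.00038 = 0.0382, or 3.8 points.
- p = 15%, n = 250: 1.96 × √0.00102 = 0.0626, or 6.3 points.
- If only 200 per arm returned the form (assumed): 1.96 × √0.000475 = 4.3 points at 5%, and 1.96 × √0.001275 = 7.0 points at 15%.
- No injuries among 250: one-sided 95% upper bound 1 − 0.05^(1/250) = 1.2%.

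**4. Power, to show what the data could not do.** Two-sided alpha 0.05, 250 per arm, using Φ{(|p2 − p1| − 1.96√(2p̄(1 − p̄)/n)) / √([p1(1 − p1) + p2(1 − p2)]/n)}, where p̄ is the mean of the two rates:

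| Assumed control rate | Power for a doubling | Rate detectable with 80% power |
|---|---|---|
| 1% | 15% | 5.4% |
| 2% | 26% | 7.3% |
| 5% | 57% | 12.0% |
| 10% | 88% | 18.8% |

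**5. Effect of the planned imputation.** Technical Considerations fills missing categorical values at random from the proportions pooled over both arms. Suppose 20% are missing in each arm and the observed rates are 10% and 5%, so the pooled rate is 7.5%. The expected rates after imputation are 0.8 × 10 + 0.2 × 7.5 = 9.5% and 0.8 × 5 + 0.2 × 7.5 = 5.5%. The difference falls from 5.0 to 4.0 points. In general it shrinks by the fraction missing, which is the wrong direction for a safety outcome.

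**The case against.** The strongest reply is that the exit form itself is not in the documents. The protocol lists topics, not items, and medical history is one of them, asked in both arms. That stands: a reader might infer that the form has no injury question, but this cannot be established. What is established is that no injury item is named and that no analysis uses the medical-history heading.

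Other stronger readings also fail:

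- *The trial cannot detect harm at all.* Tests are two-sided, and blood pressure, glucose, triglycerides, C-reactive protein and body fat can worsen. The gap is confined to injury and psychological harm.
- *Injuries reach the team only if volunteered.* The low-contact statement under Randomization describes how the intervention is delivered, not how outcomes are collected. Everyone is due a final assessment, and staff can be reached by telephone and e-mail. Systematic capture is unspecified, and the text supports no more than that.
- *A null activity result could hide benefit offset by injury.* The analysis is by intention to treat, so the net effect is the intended quantity. A yes/no injury item would not separate the two components.
- *The protocol breaks its promise.* It promises mitigation, and it supplies screening, orientation and advice.

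It can also be said that the trial is too small to study injury. This is partly right, as step 4 shows, and it is why the proposal is estimation with an interval and not a test. Finally, distress is not a named risk and the wellbeing instruments are not described. The wellbeing limb is therefore secondary, but those data are already being collected.

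**Conclusion.** The point holds as a cheap and worthwhile improvement. It is not a defect in the efficacy analysis, and no stated figure is wrong. As written, the trial would report no estimate of excess injury or psychological harm by arm, although randomisation and the existing visits make both estimable.

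The half-widths in step 3 rest on assumed rates, equal rates in the two arms and, for the 250-per-arm figures, a form from every participant. Injured participants may be over-represented among those who leave, so responders could understate the rate. Randomisation makes the comparison fair at the outset. It does not protect against differential dropout or unmasked self-report, and any difference would belong to the whole intervention package and not to the workout plan alone.

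**What to change.** 1. Add one question to the exit form, worded identically for both arms: *In the last 3 months, did you have an injury from exercise that limited your exercise for a day or more, or needed medical care?*
2. In the Data Analysis Plan, report the number and proportion injured by assigned arm and the between-arm difference with a 95% confidence interval, as a descriptive safety outcome outside the Bonferroni families.
3. Base this on observed responses, exempt it from the pooled imputation in Technical Considerations, and show how many in each arm did not return the exit form.
4. In the same table, report the change in the mental-health and wellbeing items by arm, naming the items or scales and their scoring.

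The cost is one question and one table, with no extra visit and no change to the sample size or the primary thresholds. The three-month recall window matches the one already used for the primary activity questions. The limits to state in the report are unmasked self-report, recall, and low power for uncommon injuries.
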